## 4. Introduction and Background

Our primary hypothesis is that the bubble-enhanced or BEFAST exam will be more sensitive than traditional FAST for identification of solid organ injury in hemodynamically stable blunt abdominal trauma patients when performed by emergency providers. The purpose of this study is to ascertain whether the BEFAST exam is a more sensitive screening tool than traditional FAST exam. BEFAST addresses a major limitation of conventional FAST in that it can identify lacerations to solid organs even in the absence of hemoperitoneum. Acceptance of the BEFAST exam as an appropriate alternative to CT in select situations may positively impact patient care by leading to decreased CT utilization and a change to current trauma algorithms.

Blunt abdominal trauma - whether from motor vehicle crash, assault, fall, or recreational injury - is a leading cause of morbidity and mortality [1]. According to the 2016 National Trauma Database, 12 % of all patients with trauma admissions had abdominal trauma, the majority of which is blunt [2]. The diagnosis of intra-abdominal injury due to blunt abdominal trauma can be challenging. The physical exam is unreliable in patients with altered mental status or with impairment due to drugs or alcohol. Utilization of the FAST exam has dramatically improved clinical care by enabling frontline providers to screen for injury non-invasively.

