# 11. Incidental Findings

The research team will relay any findings related to injury to solid organs and hemoperitoneum to the primary treatment team for further management. The FAST and BEFAST exams are screening exams only and not comprehensive abdominal exams; additional findings are not anticipated. If additional incidental findings are noted they will be relayed to primary treatment team for appropriate triage, referral to clinical specialists, and patient education as needed if the finding is clinically significant. All study patients will also obtain confirmatory imaging with CT study.

12. Compensation for time and effort: \$25 single payment as reimbursement for parking expenses, time, effort.

13. Statistical Analysis:

**Objective 1**: To determine if contrast-enhanced, i.e. bubble-enhanced FAST (BEFAST) outperforms non-enhanced FAST in the evaluation of solid organ injury in hemodynamically stable blunt abdominal trauma patients when performed by frontline providers using CT as gold-standard.

Descriptive Statistics. The primary results will be described using sensitivities and specificities with 95% confidence intervals. Categorical variables will be described using frequencies and percentages. Continuous variables will be described using means and/or medians as appropriate.

Primary Analyses. Agreement with the CT results will be examined using a mixedeffects/multi-level logistic regression in order to account for clustered measurements. Results from this regression will also be adjusted for the following covariates: demographics (e.g. age, sex, race), BMI, sonographer experience, contrast redosing, the presence of outward signs of injury. In the event that the logistic regression fails to estimate properly or provides poor fit to the data and/or to show consistent results across methods, alternative methods will be explored: (1) P-values and confidence intervals will be computed using a bias-corrected and accelerated bootstrapping procedure ( $\geq$ 5,000 resamples); (2) Sensitivities and specificities for BEFAST and FAST will be compared using McNemar's test.

Sample Size Calculations. Two primary issues were taken into consideration when calculating the required sample size: 1) statistical power, and 2) the expected rate of positive outcomes.

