An exam is complete if the patient tolerates the exam (no severe adverse reaction to contrast, patient allows the provider to complete the scan) and if it results in images of adequate quality to answer the focused clinical question.

Completion rates will be described as percentages with 95% confidence intervals. Assuming maximal variance for a binomial variable ( $\pi = 0.5$ ), a sample size of 187-267 (approximate) will result in 95% CIs that are no wider than  $\pm$  7.2% to 6.0%. FAST and BEFAST completion rates will be compared using either the multilevel/mixed effects logistic regression described above or McNemar's test.

**Objective 3**: To determine the interrater reliability between bedside emergency physicians and radiologists for identifying solid organ injury with BEFAST.

Inter-rater Reliability for the presence/absence of an injury will be evaluated using Cohen's or Fleiss' kappa as appropriate. The reliability of AAST scores will be evaluated using a weighted kappa statistic.

Assuming a minimal sample size of 187, the current study will have sufficient power ( $\geq$  80%) to detect reliability coefficients exceeding 0.23. For clinically relevant ratings, such as this, reliability is generally required to be high. Guidelines vary and are generally arbitrary; however, 0.8 and 0.9 are often used as cutoffs for "high" agreement, whereas a value such as 0.23 would be considered unacceptable. Thus, the current study is sufficiently powered to detect clinically acceptable levels of agreement.

14. Data and Safety Monitoring and Reporting:

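### No rule says which result decides Objective 1: the primary model tests agreement with CT, the hypothesis is about sensitivity, and the move between them can be made after the data are seen

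*Combined protocol and SAP*

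**What the plan says.** Section 4 sets the hypothesis: "Our primary hypothesis is that the bubble-enhanced or BEFAST exam will be more sensitive than traditional FAST". The sample-size text in section 13 likewise seeks power for improved sensitivity and regards a specificity difference as unlikely to be detected.

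The Primary Analyses paragraph of section 13 tests something else: "Agreement with the CT results will be examined using a mixedeffects/multi-level logistic regression in order to account for clustered measurements". A second, covariate-adjusted version follows: "Results from this regression will also be adjusted for the following covariates".

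The paragraph then provides for a change of method if the regression does not estimate properly, or if it "provides poor fit to the data and/or to show consistent results across methods, alternative methods will be explored". Two alternatives are listed. The first is a bootstrap: "P-values and confidence intervals will be computed using a bias-corrected and accelerated bootstrapping procedure". The second is: "Sensitivities and specificities for BEFAST and FAST will be compared using McNemar's test".

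No alpha is stated; the nearest statement is "The primary results will be described using sensitivities and specificities with 95% confidence intervals". The form of McNemar's test (uncorrected, continuity-corrected, mid-p or exact) is not given. Objective 2 leaves a similar choice open: "FAST and BEFAST completion rates will be compared using either the multilevel/mixed effects logistic regression described above or McNemar's test".

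**The concern.** Objective 1 asks whether BEFAST outperforms FAST, and three contrasts could answer it: pooled agreement with CT, sensitivity in CT+ patients, and specificity in CT- patients. The bootstrap is only another route to a p-value or interval. The McNemar tests replace the question.

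Of the triggers for leaving the regression, estimation failure is reasonably objective. Poor fit is a judgement made with the data in hand and has no threshold. The wish to show consistent results needs no failure at all, and nothing is said about what follows if the results are inconsistent.

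Trouble with the regression is foreseeable. The minimum of 20 CT+ patients was set for a model with two predictors, yet the adjusted model names seven covariates (age, sex, race, BMI, sonographer experience, redosing, outward signs) besides the exam effect.

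Two things are at stake. BEFAST could be declared better on a contrast that does not bear out the stated hypothesis. And the error rate of that declaration is not the one the 95% intervals suggest.

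**Working it through.** **Inputs from the documents (sections 4, 6 and 13).** Sensitivity 0.68 (standard) v 0.87 (CEUS); specificity 0.95 v 0.98; minimum n 187; planned n 267; at least 20 CT+; under 20% of abdominal CTs in blunt trauma show intra-abdominal injury.

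**Assumptions.** Two-sided 0.05 per test. CT+ counts of 20 (the minimum) and 37 (0.20 × 187 = 37.4) at n=187; 40 (0.15 × 267 = 40.05) and 53 (0.20 × 267 = 53.4) at n=267. Within-patient correlation between exams 0 to 0.5. McNemar on pooled agreement stands in for the unadjusted exam effect in the regression.

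**The plan's own figure.** The 187 cannot be reproduced, because alpha, sidedness, CT+ prevalence, within-patient correlation and the simulated test are not given. The number therefore does not reveal which contrast was meant to decide.

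**Step 1: the three tests.** Let c be the patients in whom only BEFAST agrees with CT and b those in whom only FAST does. Subscript 1 marks CT+ and 0 marks CT-.

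- Sensitivity: z = (c1 − b1)/√(c1 + b1)
- Specificity: z = (c0 − b0)/√(c0 + b0)
- Agreement: z = (c1 + c0 − b1 − b0)/√(c1 + c0 + b1 + b0)

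Agreement adds both groups, so CT- patients, who are the majority, can carry it.

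**Step 2: where the expected agreement gain comes from.** The net gain is n1 × (0.87 − 0.68) + n0 × (0.98 − 0.95).

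| n | CT+ | from sensitivity | from specificity | specificity share |
|---|---|---|---|---|
| 187 | 20 | 20 × 0.19 = 3.80 | 167 × 0.03 = 5.01 | 5.01/8.81 = 57% |
| 187 | 37 | 37 × 0.19 = 7.03 | 150 × 0.03 = 4.50 | 4.50/11.53 = 39% |
| 267 | 40 | 40 × 0.19 = 7.60 | 227 × 0.03 = 6.81 | 6.81/14.41 = 47% |
| 267 | 53 | 53 × 0.19 = 10.07 | 214 × 0.03 = 6.42 | 6.42/16.49 = 39% |

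**Step 3: how often the verdicts differ.** Paired results were simulated under the planning values, with mid-p tests.

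- n=187, 20-37 CT+: agreement and sensitivity verdicts differ in 18-54% of trials.
- n=267, 40-53 CT+: they differ in 6-31%.
- 20 CT+ of 187: agreement is significant in about 53-85% of trials, sensitivity in only 25-32%.

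If specificity is instead equal at 0.95, which is not the plan's assumption, the imbalance reverses. With 37 CT+ of 187, agreement is significant in 25-44% and sensitivity in 48-79%. Verdicts then differ in 23-40% of trials at n=187 and 36-47% at n=267.

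**Step 4: false positives if any contrast may be claimed.** Sensitivity and specificity use different patients, so two such tests give 1 − 0.95² = 9.75% two-sided. Adding the correlated agreement test gives 11.2-11.5% in large samples. In BEFAST's favour, two tests give 1 − 0.975² = 4.9%, and all three 5.7-5.8%.

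Simulated with both exams equal (0.68 and 0.95), at the sizes above:

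| McNemar form | any of three, either direction | any of three, favouring BEFAST |
|---|---|---|
| uncorrected | about 11-12% | about 5-6% |
| exact | about 4-8% | about 2-4% |

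The nominal values are 5% and 2.5%.

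**Step 5: after the fix.** With sensitivity as the only deciding contrast, over a wider set of scenarios (CT+ prevalence 10.7-30%), two-sided error is 4.1-5.3% with uncorrected McNemar and 0.4-3.4% with exact.

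**The case against.** The plan is not without order. The regression comes first under Primary Analyses and the rest are called alternatives. The named hypothesis is sensitivity, and specificity is not put forward as a route to success. Two of the triggers require a problem with the model, and the third reads most naturally as a robustness check. The a priori stopping rule also prevents analysis before enrolment is complete.

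Much of this stands, and it limits the size of the point. A reader might infer that the chance of falsely declaring BEFAST better is about twice 5%. The documents do not support that. The 11-12% figure counts results in both directions, requires the uncorrected test, which the plan does not specify, and assumes that every test is run and any significant one is claimed. A reader might also infer that the plan has no primary analysis; it has one.

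What remains is that the order points two ways: the regression is first among methods, while sensitivity is first among hypotheses. The stopping rule fixes when analysis starts, and does not settle which result decides. A robustness check with no stated consequence for inconsistency leaves the conclusion open.

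Two technical limits also stand. The mixed model, its covariate adjustment and the bootstrap were not simulated. And agreement is taken as pooled over CT+ and CT- patients: the plan describes no stratification by CT result and does not name its two predictors. The Missing Data paragraph, which codes each patient as agreeing or not, fits the pooled reading.

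**Conclusion.** The point holds as a missing decision rule combined with a mismatch of contrasts. The more serious consequence is conflicting verdicts, and it does not depend on the false-positive calculation. The conflict shrinks at the planned n of 267 but does not vanish. Only at the minimum of 20 CT+ among 187 would a claim of superiority be expected to rest mainly on specificity (57% of the expected gain).

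The error-rate consequence is secondary and bounded: at most about double the nominal 2.5% in BEFAST's favour, and near nominal with exact tests. These sizes rest on the assumed alpha, CT+ counts, correlations and McNemar stand-in. That no deciding result is named rests on the text alone. The open choice in Objective 2 is minor, since both methods compare the same completion rates.

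**What to change.** In section 13, Objective 1:

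1. State that Objective 1 is decided only by the paired BEFAST-FAST difference in sensitivity among CT+ patients, at two-sided 0.05, with one named test. If that is McNemar's, give its form.
2. Replace the poor-fit and consistency triggers with a fixed rule: a substitute named in advance, used only on objective failure of the deciding analysis (for example non-convergence or separation), and testing the same contrast.
3. Label the agreement regression (unadjusted and adjusted), the bootstrap and the specificity comparison as supportive, and state that a conflicting supportive result does not change the conclusion.
4. For Objective 2, name one test.

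This costs a few sentences and needs no new data or patients. The downside is that a favourable supportive result can no longer rescue a non-significant primary one.

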1) Power calculations were based on previous studies examining the sensitivity and specificity on standard and contrast-enhanced ultrasound. The results from these studies were meta-analyzed (fixed-effects, inverse-variance method) and indicated that (1) the sensitivity for CEUS (lower limit = 0.87) is greater than the sensitivity for standard ultrasound (upper limit = 0.68); and (2) the specificity for CEUS (0.98) is similar to the specificity for standard ultrasound (0.95). This analysis aimed to ensure that the present study has sufficient power to show improved sensitivity when using CEUS. Note that, because this sample size calculation uses the lower limit of the CEUS estimate and the upper limit of the standard ultrasound estimate, actual power will likely be greater. Given the small meta-analytic difference in specificities between methods, it is unlikely that differences in specificity will be detected. These values were used to estimate the sample size required to achieve 80% power using Monte Carlo simulations (10,000 samples) implemented in R v3.4.1. This analysis determined that the sample size would need to be at least 187.

2) Using the rule of thumb 10 positive results for each predictor, we aimed to ensure that there will be a sufficient number of positive results for a model with two predictors (i.e. at least 20 positives. Thus, the current study will aim for a sample size of at least 187; however, data collection will not end until at least 20 CT+ patients are enrolled. Importantly, this stopping rule is entirely a priori and ceasing data collection will not be dependent on any statistical analyses, significance tests, or interim analyses. No analyses will be conducted until after this stopping rule is reached.

Missing Data. In the event of substantial missing data, data will be imputed using a multiple imputation procedure. The type of procedure and the number of imputed data sets will be determined by the amount of missing data and the pattern of missingness. As a sensitivity analysis, we will 1) assume the worst and assign a "does not agree" outcome for that patient and 2) assume the best and assign an "agrees" outcome for that patient. These analyses will describe the boundary conditions for the models described above.

**Objective 2**: To determine whether emergency physicians can incorporate BEFAST evaluation at the point-of-care in a trauma evaluation of a hemodynamically stable adult blunt abdominal trauma patient.

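### The floor of 20 CT-positive patients is sized for two predictors, but the regression under Primary Analyses carries about eight, and the plan does not say which model is primary

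*Combined protocol and SAP*

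**What the plan says.** Section 13, Objective 1, Sample Size Calculations, item 2, bases the floor on a rule of thumb: "Using the rule of thumb 10 positive results for each predictor". The stated aim is "a sufficient number of positive results for a model with two predictors (i.e. at least 20 positives", and the stopping rule follows from it: "data collection will not end until at least 20 CT+ patients are enrolled". The two predictors are not named.

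Under Primary Analyses in the same section, the model is described so: "Agreement with the CT results will be examined using a mixedeffects/multi-level logistic regression". The next sentence begins "Results from this regression will also be adjusted for the following covariates" and lists "demographics (e.g. age, sex, race), BMI, sonographer experience, contrast redosing, the presence of outward signs of injury". No base model is separated from an adjusted one, and neither is ranked above the other.

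A fallback follows, opening with "In the event that the logistic regression fails to estimate properly or provides poor fit to the data". It offers a bias-corrected and accelerated bootstrap and McNemar's test.

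**The concern.** The sizing text and the analysis text describe different models. One calls 20 positives sufficient for two predictors. The other fits seven covariates in addition to the exam comparison. If the adjusted regression is the primary analysis, the only sample the stopping rule guarantees falls well short of the plan's own standard for it.

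The rule also counts CT-positive patients, whereas the regression models agreement with CT. In a logistic model the scarcer outcome category limits what can be fitted, and here that is disagreement.

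At stake is whether the adjusted estimate can be obtained reliably. Because no order of models is given, it is also open which result would count as the trial's answer if the adjusted model failed or differed from a simpler one.

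**Working it through.** **Inputs.** From section 13: 10 positives per predictor; two predictors; floor of 20 CT-positive; minimum of 187 patients; sensitivity 0.87 (BEFAST) and 0.68 (FAST); specificity 0.98 and 0.95. From sections 6 and 9: 267 patients. The documents state no design prevalence. Section 4 says only that fewer than 20% of abdominal CTs in blunt trauma show intra-abdominal injury, so 10% to 20% is used as an assumed range.

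**1. The plan's figure.** 10 × 2 = 20. Reproduced.

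**2. The same rule for the listed model.**
- Exam type + age, sex, race, BMI, sonographer experience, redosing, outward signs = 8 terms, each counted as one coefficient: 10 × 8 = 80. The floor gives 20/8 = 2.5 per predictor.
- Without the three demographics, which are given only as examples: 5 terms, 10 × 5 = 50.
- Race or experience with more than two levels raises the need; 10 coefficients would need 100.

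**3. CT-positive patients expected (N × prevalence).**

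| Assumed prevalence | N = 187 | N = 267 |
|---|---|---|
| 10% | 19 | 27 |
| 15% | 28 | 40 |
| 20% | 37 | 53 |

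At 20%, the binomial chance of 80 or more among 267 is about 0.00007. An expected 80 needs 80/0.20 = 400 patients, or a prevalence of 80/267 = 30%. The five-term count of 50 is reached at 267 only at the top of the assumed range.

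**4. Disagreements, the modelled event.** Expected number per exam = (1 − sensitivity) × CT-positive + (1 − specificity) × CT-negative.
- 187 patients, 20 CT-positive: FAST 0.32 × 20 + 0.05 × 167 = 14.75; BEFAST 0.13 × 20 + 0.02 × 167 = 5.94; total 20.7. That is 10.3 per predictor for two and 2.6 for eight.
- 267 patients, 53 CT-positive: FAST 27.66 + BEFAST 11.17 = 38.8, or 4.9 per predictor for eight.

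**5. Effect of the patient-level covariates on the exam term.** Simulation of the all-patient model at 187 patients with 20 CT-positive, assuming covariates unrelated to agreement, no random effect, and exam type with or without six patient-level covariates. The true log odds ratio is ln[(181.06/5.94)/(172.25/14.75)] = 0.959. One set of 4,000 runs gave means of 1.014 without and 1.032 with the covariates (SD 0.536 and 0.545; 0.3% not estimable). A separate set gave 1.04 and 1.06 (0.5% not estimable). Both shifts are about 2%.

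**6. Redosing.** Redosing can occur only with BEFAST. If no redosed exam disagrees with CT, its coefficient has no finite estimate. With redosing rate r, taken as unrelated to accuracy, the chance of this is (1 − 0.13r)^20 × (1 − 0.02r)^167:
- r = 10%: 0.55
- r = 20%: 0.30
- r = 50%: 0.05. The mirror case, with no disagreement among non-redosed BEFAST exams, adds about another 0.05.

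Three-level race alone gave separation in about 5% of simulated runs. With both terms in the model, separation was about 55%, 35% and 15% at r = 10%, 20% and 50%. The documents give no redosing rate.

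**The case against.** Five points deserve weight.

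- **Fallback.** The plan provides for failure of the regression. McNemar's test is a valid paired comparison without covariates, and the sensitivities and specificities with confidence intervals are reported whatever the regression does. This softens the consequence. It does not reconcile the two texts, because the fallback is chosen only after the fit has been seen and its trigger is not defined.
- **Wording.** Saying that results will also be adjusted can mean a small model followed by an adjusted one, and the two-predictor remark would suit that small model. This is a fair reading. The defect then is that no hierarchy is stated.
- **A minimum, and a rule of thumb.** More than 20 CT-positive patients may well accrue, and 10 per predictor is not a hard limit. But 20 is all that the stopping rule guarantees, and the rule is the plan's own reason for calling it sufficient.
- **Event count.** Counting disagreements does not undermine the floor for two predictors: 20.7 events meet it.
- **Use of the covariates.** Each patient has both exams, so patient-level covariates have little to correct in the exam contrast. Outward signs are a possible exception: section 6 has the investigator record them as a possible influence on the reading, so they could act differently by exam.

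A reader might go further and infer that adjustment would seriously inflate the exam effect. Simulations confined to CT-positive patients did show this: a mean log odds ratio of about 1.47 against a true 1.147 with seven terms, and separation in about 80% of runs once redosing and three-level race were added. The plan does not state a fit restricted to CT-positive patients. It models agreement with CT, and in the all-patient model the shift is about 2%.

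**Conclusion.** The inconsistency holds and should be fixed. By the plan's own rule the floor of 20 supports two predictors, against about 80 positives for the listed model and 50 on the most lenient count. The planned 267 patients would not be expected to reach 80 at a prevalence of 10% to 20%. On the event actually modelled, the guaranteed sample offers about 21 disagreements, or 2.6 per predictor for eight.

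The consequence is limited. The documents do not support saying that the exam effect would be materially biased or that the primary comparison could not be made. The patient-level covariates do little harm to the exam term. The real estimability risk is redosing, with separation in roughly 15% to 55% of runs over assumed rates of 50% down to 10%. Because redosing exists only with BEFAST, adjusting for it also turns the exam coefficient into non-redosed BEFAST versus FAST, which is not the stated question.

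These results rest on the plan's accuracy figures, an assumed prevalence and redosing rate, covariates unrelated to agreement, and no random effect in the simulations.

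**What to change.** In section 13, Primary Analyses:
- Name the small model as the primary analysis: exam type, at most one further term, and patient as the grouping factor.
- Label the covariate-adjusted model secondary or exploratory.
- Leave redosing out of any model that estimates the BEFAST-versus-FAST contrast.

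In section 13, Sample Size Calculations, item 2:
- Say that 20 positives supports only the small model.
- State the per-predictor rule for disagreements with CT.

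If the trial later fits the small model in CT-positive patients alone, it should note that 0.32 × 20 + 0.13 × 20 = 9 misses are expected at the floor, or 4.5 per predictor for two terms.

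The cost is wording, with no extra patients. The adjusted estimate loses primary status, and any exam-specific effect of outward signs is examined only in the secondary model.

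### The planned worst-case and best-case analyses bound each exam's own agreement with CT but do not, as labelled, bound the BEFAST–FAST contrast once a FAST outcome is missing

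*Combined protocol and SAP*

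**What the plan says.** All of this is in section 13 (Statistical Analysis) of the combined protocol and SAP, under Objective 1.

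- **Aim.** "To determine if contrast-enhanced, i.e. bubble-enhanced FAST (BEFAST) outperforms non-enhanced FAST in the evaluation of solid organ injury", with CT as the reference. Section 6 has both exams done in the same patient, the baseline FAST first.
- **Primary Analyses.** "Agreement with the CT results will be examined using a mixedeffects/multi-level logistic regression in order to account for clustered measurements". Among the alternative methods: "Sensitivities and specificities for BEFAST and FAST will be compared using McNemar's test".
- **Missing Data.** Multiple imputation is planned if missingness is substantial. The sensitivity analysis will first "assume the worst and assign a 'does not agree' outcome for that patient" and then "assume the best and assign an 'agrees' outcome for that patient". Of the two together the plan says: "These analyses will describe the boundary conditions for the models described above".

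The rule does not say which exam's outcome is filled. No scenario gives BEFAST and FAST opposite values.

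**The concern.** The quantity of interest is a difference between two exams in the same patient. Filling both sides with the same value moves both rates together and leaves the difference largely where it was. Filling a missing FAST with disagreement penalises the comparator, so the scenario called worst flatters the new exam.

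The results are to be presented as boundary conditions. Two near-identical results could then be read as showing that missing data cannot alter the comparison, when the damaging configuration was never examined. The CT-positive group may be small (enrolment continues until there are at least 20), so a few patients can move the sensitivity difference a long way.

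**Working it through.** The plan gives no figure for this analysis, so there is none to reproduce. The check is algebra followed by illustrations.

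**Notation.** N patients; x_B and x_F observed agreements with CT for BEFAST and FAST; m_B and m_F missing outcomes for each exam. The contrast is d = (BEFAST agreements − FAST agreements)/N.

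- Planned worst: d = (x_B − x_F)/N
- Planned best: d = (x_B + m_B − x_F − m_F)/N
- Least favourable attainable: d = (x_B − x_F − m_F)/N
- Most favourable attainable: d = (x_B + m_B − x_F)/N

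The planned pair spans |m_B − m_F|/N; the attainable range spans (m_B + m_F)/N. Hence:

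- only BEFAST missing (m_F = 0): the planned pair gives the true bounds;
- only FAST missing (m_B = 0): the two endpoints are reached, but with the labels reversed;
- both exams missing in m patients: the planned span is 0 and the attainable span is 2m/N;
- any other mixture: the planned span is too narrow.

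**Inputs for illustration.** From section 13: N = 187, sensitivities 0.87 and 0.68, specificities 0.98 and 0.95, at least 20 CT-positive patients. Assumed: 20% prevalence (section 4 says only that fewer than 20% of such CTs show injury) and all missing counts. Expected agreement is then 0.2×0.87 + 0.8×0.98 = 0.958 for BEFAST and 0.2×0.68 + 0.8×0.95 = 0.896 for FAST. Observed agreements are these rates times the number observed, rounded. Differences are in percentage points.

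| Assumed missing | x_B, x_F | Planned worst | Planned best | Least favourable | Most favourable |
|---|---|---|---|---|---|
| 19 both | 161, 151 | 10/187 = +5.3 | 10/187 = +5.3 | −9/187 = −4.8 | 29/187 = +15.5 |
| 9 BEFAST only, 9 others FAST only | 171, 159 | 12/187 = +6.4 | 12/187 = +6.4 | 3/187 = +1.6 | 21/187 = +11.2 |
| 19 BEFAST only, 9 others FAST only | 161, 159 | 2/187 = +1.1 | 12/187 = +6.4 | −7/187 = −3.7 | 21/187 = +11.2 |
| 9 FAST only | 179, 159 | 20/187 = +10.7 | 11/187 = +5.9 | 11/187 = +5.9 | 20/187 = +10.7 |
| 19 BEFAST only | 161, 168 | −7/187 = −3.7 | 12/187 = +6.4 | −7/187 = −3.7 | 12/187 = +6.4 |
| Sensitivity: 2 both, of 20 CT-positive | 16, 12 | 4/20 = +20 | 4/20 = +20 | 2/20 = +10 | 6/20 = +30 |

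The gap for patients missing both does not depend on prevalence or accuracy: 2m/187 is 5.3 points for m = 5, 10.7 for m = 10 and 20.3 for m = 19.

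**McNemar's test (exact, two-sided; assumed counts).**

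- *Ten patients missing both exams, 14 v 5 discordant pairs otherwise.* Both planned scenarios add only concordant pairs, so both give 14 v 5, p = 0.064. The extremes are 24 v 5 (p = 0.0005) and 14 v 15 (p = 1.0).
- *37 CT-positive patients (20% of 187).* In 31 complete pairs, 19 are detected by both exams, 8 by BEFAST only, 1 by FAST only and 3 by neither. Three more lack BEFAST (FAST detects 2) and three lack FAST (BEFAST detects all 3). Planned worst is 11 v 3 (p = 0.057) and planned best 9 v 1 (p = 0.021), each a difference of 8/37 = 21.6 points. The attainable bounds are 8 v 3 (5/37 = 13.5 points, p = 0.227) and 12 v 1 (11/37 = 29.7 points, p = 0.003).

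**Missing CT.** Suppose 5 patients lack CT and both exams are scored on one positive/negative call: 3 read BEFAST+/FAST− and 2 read BEFAST−/FAST+. Setting every CT positive gives BEFAST a net 3 − 2 = +1 agreement; setting every CT negative gives −1. Choosing CT patient by patient reaches +5 and −5. A blanket setting is therefore not a bound either.

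**The case against.** - **The rule works in what may be the commonest case.** FAST is done first, so a stopped session or a contrast reaction leaves BEFAST alone missing, and there the planned pair is correct. This stands. But the rule is not confined to that case. Section 6 sets minimum FAST views and makes completion depend on image quality, and Objective 2 plans to compare completion of the two exams, so incomplete FAST exams are foreseen.
- **The text never says that the contrast is what is bounded.** It refers to the models, and section 13 describes the primary results as sensitivities and specificities. The scenarios do bound each exam's own agreement rate, which is a reason to keep them. The models, however, serve a comparison, so a reader will take the bounds to cover it. If BEFAST alone was meant, the text should say so.
- **A reader might infer that the planned analyses would generally hide a fragile result.** The calculations do not support that. In the 37-patient example their p-values fall on either side of 0.05, which would itself signal fragility, and with unequal missingness the planned difference moves (+1.1 to +6.4 in the third row of the table).
- **A reader might infer that one value for both exams is impossible when CT is missing and the reads differ.** That holds only if both are scored on one shared binary call. Section 6 gives FAST a free-fluid question and BEFAST a solid-organ question, and findings are recorded by organ, so the documents do not establish it. Missing CT may also be rare: a planned CT is an inclusion criterion, and section 11 expects every patient to have one.
- **Concordant pairs are uninformative only for McNemar's test.** In the mixed model they can affect variance terms. Same-value filling still does not produce the extremes of the contrast.

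**Conclusion.** The point holds within limits. As written, the two scenarios bound each exam's agreement rate, and they bound the contrast when only BEFAST is missing. Once FAST outcomes are missing they do not serve as labelled bounds on the contrast: the range collapses or is too narrow when outcomes are missing for both exams, and the labels reverse when FAST alone is missing.

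The shortfall in range is (m_B + m_F − |m_B − m_F|)/N. It is 20.3 points for 19 of 187 patients missing both exams, and 20 points of sensitivity for 2 of 20 CT-positive patients. These counts are assumed, and the documents give no expected missing rate by exam. The figures are crude rate differences; the adjusted mixed-model estimate will differ in scale.

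This concerns a sensitivity analysis behind multiple imputation. It does not invalidate the primary analysis, but the stated purpose of the sensitivity analysis is not met for the study's main question.

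**What to change.** In section 13, Objective 1, Missing Data:

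1. Keep the two planned scenarios, described as bounds on each exam's own agreement rate.
2. Add two for the contrast. Least favourable: missing BEFAST counted as disagreeing and missing FAST as agreeing. Most favourable: the reverse. Report the difference and p-value for sensitivity among CT-positive and specificity among CT-negative patients.
3. Where CT is missing but both exams were read on the same binary call, set CT for each patient to the value that disfavours BEFAST, then to the value that favours it, and derive each exam's agreement from its recorded read. Do not set all missing CTs positive and then all negative. For concordant reads the CT value leaves the difference in overall agreement unchanged but alters the CT-positive and CT-negative denominators, so state how these patients are allocated.
4. State which exam's outcome each rule fills.

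The cost is a few sentences, two extra model runs and wider reported bounds. No new data are needed.
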